### **3. Study Design**

**3.3.** This project will use a mixed methods research design to determine the feasibility and impact of a brief, MI-Guided Shame Resilience intervention on well-being, shame intensity, shame resilience, willingness to communicate, and

treatment attendance. Data will be collected in person by survey and interview at baseline and either in-person or over the phone at 1-month follow-up. Although a controlled, between group design was considered for the current study, in consultation with Co-Investigators and Milagro providers and staff, we elected to conduct a within groups evaluation, to maximize our ability to refine and investigate the acceptability of the intervention. Within group changes in outcomes can be used to estimate effect sizes for a larger trial.

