### **Aim 1: Assess the feasibility of study methods (recruitment and retention), intervention fidelity, and treatment satisfaction.**

We will track rates of participation in the study as well as retention at follow-up. All intervention sessions will be audio-recorded and rated using the Motivational Interviewing Treatment Integrity tool. Participants will provide quantitative ratings of treatment satisfaction. In addition, a random sample of ten participants will be invited to complete qualitative interviews on treatment satisfaction.

Hypotheses: The study sample will be recruited during the study timeline and a  $\geq 85\%$  follow-up rate will be attained. Coded intervention samples will meet benchmarks for proficiency on a validated treatment fidelity rating tool. Participants will report high satisfaction with the intervention.

**Aim 2: Examine the preliminary effectiveness of the intervention on well-being, shame, shame resilience, and treatment attendance.** We administer a battery of validated questionnaires at baseline and 1-month follow-up. We will analyze within-group changes in effectiveness outcome variables. Standardized measures of effect size will be calculated.

Hypotheses: The intervention will lead to significant improvements in well-being, shame, shame resilience, and treatment attendance.

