**2.2** The PI has dedicated her career to the development and evaluation of brief applications of MI, including a clinical trial focused on risky alcohol use in a recently completed K23 award (K23 AA020865;) and another soon to be completed multi-site clinical trial focused on unintended pregnancy prevention from an R01 level grant (TP2AH000028;). The current proposal bridges the PI's background in addictions and pregnancy and targets a new health behavior in shame resilience. Pilot data demonstrating feasibility and initial efficacy will be needed in order to secure a larger grant. Co-Investigator [name] is the Medical Director of the Milagro Clinic. He will shortly be conducting a sabbatical at X in which he will be focusing on treatments for shame and trauma with this clinical population. He has previously worked on treating infants who were exposed to substances during pregnancy as well as researching treatment programs of pregnant women with past trauma and substance abuse. Project Coordinator, [name], also has extensive experience relevant to shame resilience and motivational interviewing, making him ideal to carry out the study intervention and evaluation aspects of the proposal. [name] recently graduated with honors from UNM's psychology department, where his senior thesis, which is currently under review for publication found a significant association between shame resilience and well-being, providing support for the theoretical mechanisms underlying shame resilience theory. [name] has worked extensively with the PI for the past year and is skill MI interventionist.

**2.3.** [name] recently graduated with honors from UNM's psychology department, where his senior thesis, which is currently under review for publication found a significant association between shame resilience and well-being, providing support for the theoretical mechanisms underlying shame resilience theory.

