Brief-Intervention: Twenty participants will receive a brief, MI-Guided Shame Resilience intervention. Participants will attend a one-on-one intervention with the research coordinator. The intervention will be 20-30 minutes and will be conducted in style consistent with MI. Participants will be invited to discuss their own experience with shame and how it affects them before moving into a collaborative discussion in which shame resilience strategies are introduced and practiced. The interventionist will help guide the conversation and incorporate shame resilience into the participants' own life.

All participants will receive the brief-intervention as there currently no alternative treatments or procedures for issues of shame.

Follow-up Data Collection: Telephone or in-person follow-up surveys at one month after receiving the intervention. In-person follow-ups will occur at a patients' scheduled visit to the clinic. Data collection will be surveys completed on a tablet device for privacy and security. If follow-up occurs over the phone, the interventionist will work with the participant to establish an adequate time, during the initial visit.

**12.3** We are not collecting existing or prospective data.

**12.4** Participant recruitment, consent, baseline measurements, and intervention will occur at the South East Heights clinic. Participant follow-up will occur over the phone or at the South East Heights Clinic. Data analysis will occur at the department of Family and Community Medicine.

**12.5** After completing the informed consent process participants will complete five instruments before the intervention to measure the preliminary effectiveness of the intervention. Participants will complete the instruments again during the 1-month follow-up phone call.

1. The *Measure of Subjective Well-Being* is short, five-item survey with Likert response options for subjective quality of life based on positive mood, vitality, and general interest. The tool was developed by the World Health Organization and has strong psychometric characteristics.

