To address Aim 2: Within group changes in targeted outcomes including well-being, shame, shame resilience, willingness to communicate about health, and treatment attendance. We will analyze the within-group data using one sample t-tests comparing baseline and follow-up means for each measure. In addition, we will calculate standardized effect sizes comparing baseline and follow-up scores, using Cohen's d. Exploratory analyses will compare all measures using a correlation matrix at both baseline and follow-up, particularly looking at the interaction between shame resilience and each measure.

Fidelity and Quality: The research coordinator will meet with the study PI, a clinical psychologist, weekly for clinical supervision during the intervention phase of the study. All sessions will be audio-recorded and scored by the PI using an established MI fidelity rating tool called the Motivational Interviewing Treatment Integrity Scale 4.2.1.

**13.4** The main purpose of this Pilot is to assess feasibility for a future clinical trial. Data from this pilot will be used in a future power analysis.

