## **19 Potential Benefits to Subjects**

**19.1** Participants involved in the study will receive a brief intervention in addition to standard care and may benefit from the effects of either. However, no proven direct health benefits will accrue to the research participants. If this research is successful, then the patients may benefit from new program developments based on the findings, but this is in the future.

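### Uncontrolled pre-post change is offered as an effect size for a larger trial and credited to the intervention; with no comparison group it can over- or understate the between-arm effect

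*Combined protocol and SAP*

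**What the plan says.** Section 3.3 records that a controlled between-group design was considered and not adopted: "we elected to conduct a within groups evaluation, to maximize our ability to refine and investigate the acceptability of the intervention". It then states, without qualification: "Within group changes in outcomes can be used to estimate effect sizes for a larger trial".

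Section 12.2 confirms that nobody goes untreated: "All participants will receive the brief-intervention as there currently no alternative treatments or procedures for issues of shame". Section 19.1 says that participants "will receive a brief intervention in addition to standard care and may benefit from the effects of either".

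The analysis for Aim 2 (section 13.3) is a one-sample t-test of baseline against follow-up for each measure. It adds: "we will calculate standardized effect sizes comparing baseline and follow-up scores, using Cohen's d". The SD to be used for d is not named. Section 13.4 then says: "Data from this pilot will be used in a future power analysis". It does not list the quantities, so section 3.3 is the only guidance on the effect size.

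On attribution, the Aim 2 hypothesis in section 1 reads: "The intervention will lead to significant improvements in well-being, shame, shame resilience, and treatment attendance". Section 2.2 gives the intended use: "Pilot data demonstrating feasibility and initial efficacy will be needed in order to secure a larger grant".

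No section names the missing comparison group as a limit on the effect size or on attribution. None plans an external control, a correction or a sensitivity range.

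**The concern.** A controlled trial is sized on the difference between arms. Pre-post change in a single treated group equals that difference only if a comparison group would not have changed. Several things could move the scores here without the intervention. Participants are in medication assisted treatment and in the first or second trimester (section 4.4), so both care and pregnancy progress over the month. The questionnaires are repeated. Baseline is in person, while follow-up may be by telephone (section 3.3). Section 19.1 itself accepts that benefit may come from standard care.

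Two things are at stake. If the pre-post d is carried into the later power calculation as the between-arm effect, that trial will be too small if usual-care patients also improve, and larger than needed if they worsen. In the pilot itself, a significant t-test could reflect non-specific change alone, yet the Aim 2 hypothesis would read it as an intervention effect.

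**Working it through.** **Inputs from the documents.** One group of 20 (section 5.2), all treated (section 12.2). Target follow-up is at least 85% (Aim 1), so 0.85 × 20 = 17 completers. The sample size rests on a cited criterion. No alpha, power, effect size, SD, usual-care change or pre-post correlation is given, so there is no power calculation to reproduce.

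**Assumptions.** Two-sided 5%, 80% power, 1:1 allocation in the later trial, and an example pre-post d of 0.5 on the scale of that trial's analysis. The usual-care change c is varied; positive means improvement.

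**1. Sizing the later trial.** True between-arm effect = pre-post d − c. Power is that of the two-sample t-test: noncentral t with 2n − 2 degrees of freedom and noncentrality δ√(n/2), where δ is the true effect and n the number per arm. Taking d = 0.5 at face value gives 64 per arm.

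| Usual-care change c | True effect 0.5 − c | Power with 64 per arm | n per arm needed |
|---|---|---|---|
| −0.2 | 0.7 | 98% | 34 |
| 0 | 0.5 | 80% | 64 |
| +0.2 | 0.3 | 39% | 176 |
| +0.3 | 0.2 | 20% | 394 |

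A normal-approximation formula gives one fewer per arm (33, 63, 175, 393) and the same power figures to the nearest percent.

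**2. Attribution within the pilot.** Assume no intervention effect and a background improvement of m SDs of change. The one-sample t-test on n = 17 has 16 degrees of freedom and noncentrality m√17. The probability of a significant result in the favourable direction, for each test, is:

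- m = 0: 2.5%
- m = 0.3: 21%
- m = 0.5: 49%

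**3. Precision.** An observed d of 0.5 on the SD of change gives t = 0.5 × √17 = 2.06. Inverting the noncentral t gives a 95% CI for d of −0.01 to 1.00. This reflects the small sample, not the missing comparator, but it is a second reason not to plan on the point estimate.

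**4. The unnamed standardiser.** Suppose d = 0.5 is on the SD of change, with equal SDs at both visits and pre-post correlation r. Then:

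- on the raw follow-up SD, d_raw = 0.5 × √(2(1 − r));
- for ANCOVA, d_ANCOVA = d_raw / √(1 − r²).

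| r | d_raw | n per arm, raw follow-up | d_ANCOVA | n per arm, ANCOVA | n per arm, change score |
|---|---|---|---|---|---|
| 0.3 | 0.592 | 46 | 0.620 | 42 | 64 |
| 0.5 | 0.500 | 64 | 0.577 | 49 | 64 |
| 0.7 | 0.387 | 106 | 0.542 | 55 | 64 |
| 0.8 | 0.316 | 158 | 0.527 | 58 | 64 |

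So the same reported d leads to different trial sizes. Without the SDs and the correlation it cannot be moved to the raw-score or ANCOVA scale.

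**The case against.** The strongest reply is that the documents claim less than this. Section 3.3 says the changes can be used, not that the pre-post d will be entered as the between-arm difference. Effectiveness is called preliminary throughout, section 13.4 gives feasibility as the main purpose, and the single-group choice is explained. A hypothesis is an expectation, not a decision rule. Every input to the sample-size illustration is assumed, and any harm would arise in a later protocol.

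Part of this stands. A single-arm pilot suits Aim 1, and no control arm is called for. The figures show what could happen, not what is likely. Repeat questionnaires cannot explain a change in attendance, which comes from medical records (section 13.3). The standardiser is a side issue that any paired analysis would share, and d on the SD of change can be recovered as t/√n if both are reported.

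None of it supplies the missing caveat. Permissive wording and the word preliminary do not tell a reader that the change is not a between-arm effect. The hypothesis carries no hedge about cause. Informing a larger trial is a stated purpose of this pilot, so guidance that points to the wrong planning quantity matters here. That the direction of bias is unknown is a further reason not to use the number as a treatment effect.

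**Conclusion.** The concern holds and should be fixed. As written, section 3.3 offers uncontrolled change as an effect size for a larger trial, and Aim 2 attributes that change to the intervention. The design cannot separate the intervention from standard care, time or retesting. On the assumed example of d = 0.5, a usual-care change between +0.3 and −0.2 moves the requirement from 394 to 34 per arm, against 64 planned, and power from 20% to 98%. These figures rest on assumed effects, two-sided 5% and 80% power; the direction of the error cannot be known from the documents. Confidence is high on what the text says and on the logic; the illustrated sizes are examples only. Aim 1 is untouched.

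**What to change.** - **Sections 3.3 and 13.4.** Replace the last sentence of 3.3 and extend 13.4 along these lines: *Within-group change will not be used as the treatment effect when planning the larger trial. The pilot will supply outcome SDs, the pre-post correlation, and recruitment and retention rates. The target will be the smallest worthwhile between-arm difference.* If no such difference can yet be set for a scale, the minimum is to state that pre-post d is not a between-arm effect, and to plan on a justified difference with a sensitivity range for usual-care change.
- **Section 13.3, Aim 2.** Report mean change and d with 95% CIs. Name the SD that standardises d, and give the baseline SD, the SD of change and the pre-post correlation.
- **Section 1, Aim 2 hypothesis.** Reword it as estimating change from baseline, without attributing the change to the intervention.

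The cost is wording in sections 1, 3.3 and 13. No new data, procedures or participant burden are needed. The Aim 2 claim becomes more modest, which also tempers what section 2.2 can promise about initial efficacy in a grant application.

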#### **4. Inclusion and Exclusion Criteria**

**4.3.** 20 Milagro participants will be recruited to participate in the intervention and follow-up. Participants will be screened and consented during regular medical visits at the South-East Heights clinic and the Family and Community Medicine (FCM) Clinic at [name]. During recruitment, all patients attending the clinic for standard services will be approached by a research team member in the waiting or exam room. The research team member will ask the patient if they are interested in learning whether they are eligible to participate in a study.

**4.4.** Inclusion criteria: Study participants will be Milagro patients, engaged in medication assisted treatment, at least 18 years of age, can read and speak English, are willing to be contacted for follow-up, are not incarcerated, and are within the first or second trimester of pregnancy

4.3 We will be including pregnant women in the sample.

**4.5.** Exclusion criteria: The study will not enroll non-English speaking Milagro patients, patients with obvious cognitive impairments, or those with the inability to provide informed consent.

#### **5. Number of Subjects**

**5.1** This is not a multi-center study.

**5.2** We will recruit participants at the South-East Heights Clinic and the FCM Clinic

We will recruit 20 participants for the pilot study.

**5.3** The sample size for this pilot study is based on the criteria set forth by [name] in 1995. The South-East Heights and FCM clinics provides health services to the Milagro population.

#### **6. Study Timelines**

**6.1** Individual participants will participate for a duration of one month. After the initial encounter we will follow-up with participants at the end of a one-month period. The duration for enrolling all subjects will be ten months, the duration for investigators to complete the analysis will be twelve months.

#### **7. Study Endpoints**

**7.1** The primary endpoint for the study is December 2020, the secondary endpoint is February 2021

7.2 There are no safety endpoints to report.

7.3. There are no exploratory endpoints to report.

## 8. Research Setting

8.1 Research will be conducted in University of New Mexico South East Heights Family Medicine Clinic and the FCM Clinic.

8.2 Potential subjects will be identified and recruited at the South East Heights Clinic and FCM Clinic. As described in section 4.1, recruitment strategy 1 will involve inviting patients at the clinic to complete an eligibility screening form.

Research procedures will be performed at the South East Heights Clinic and FCM Clinic. Including: recruitment, screening, consent, baseline assessment, and completion of brief intervention. Follow-up interviews will be conducted either via telephone or in person. Analysis will be conducted in offices at the University of New Mexico Health Sciences Center.

8.3. We will not have a formal community advisory board, although throughout the project period, we will engage community groups and advocacy organizations for their support and input.

8.4. NA, no research will be conducted outside of UNM HSC or its affiliates.

## 9. Resources Available

9.1 The PI and study staff have extensive experience which prepares them to conduct the proposed study.

Principal investigator [name], is an associate professor in the department of family and community medicine. She works closely with the research management team and is currently the PI on the TEMPO study, and as such has experience managing a multidisciplinary research team delivering a brief intervention using motivational interviewing. This research question is of high clinical relevance to her and will lay the groundwork for future research into establishing programs of care. [name] will supervise all study activities.

[name], MPH, will serve as a co-investigator and clinic liaison. [name] is the medical director of the maternal child health program for the department of family and community medicine. [name] has a proven track record for the coordination and care of maternal health research and patients. He has been the lead investigator on several studies that promote maternal health. [name] will be responsible for medical-related issues should they arise.

[name], BS, will serve as research coordinator for the current project. [name] is a research coordinator in the Department of Family and Community Medicine at the University of New Mexico Health Science Center. [name] has a proven track record in the coordination, data collection, and analysis of shame research. He has participated in several studies that recruit, provide a brief intervention, and follow-up participants. [name] currently serves as a research coordinator on the TEMPO study. This brief intervention research study includes motivational interviewing and multiple follow-up surveys, both telephone and in-person. [name] has also mentored family medicine residents in the UNM Department of Family and Community Medicine in motivational interviewing related activities.

**9.2** All medical procedures will be conducted as part of standard care by site clinicians. However, [name] is a licensed physician and will be responsible for any emergent medical decision-making associated with the project.

**9.3** Recruitment Feasibility: There are 250 potential subjects within the Milagro population. We need to recruit 8 percent over a ten-month period.

Time Committed: The project is anticipated to take one year to complete.

*Facilities:* The University of New Mexico Health Sciences Center (HSC) is the largest academic health complex in the state of New Mexico and has the only medical school in the state. With its internationally recognized track record for conducting cutting-edge and community engaged health research, the UNM HSC is an ideal setting for a research project of this size and scope. The UNM HSC provides extensive support for the management of projects including infrastructure, grants and contract management, IT and library service, and educational opportunities for faculty and staff. The project offices will be housed in the HSC Department of Family and Community Medicine (FCM). FCM is currently ranked 3rd nationally in federal funding among all departments of Family Medicine. The department is known for our commitment to increasing strategies to eliminate barriers to health equity. FCM will provide office space, desktop computers, grants management and other administrative support to facilitate the success of the project. The Department Chairman, [name] is highly supportive of this project.

Availability of Medical or Psychological Resources: All participants will have full access to all standard care services at South-East Heights Clinic.

Process to Ensure Protocol Knowledge among Study Personnel: All study staff and investigators, will be asked to read this IRB proposal in its approved form.

Weekly team meetings will be held for staff to review study procedures. All study personnel will complete required CITI training.

## **10 Prior Approvals**

**10.1** We obtained a letter of support from [name], the Medical Director of the Milagro population. Which will be included with our supporting documents.

**10.2** We have included the Departmental Review Form with our supporting documents

**10.3** Ionizing radiation is not included in this study.

**10.4** Biological specimens and drug attachment are not included in this study.

## **11 Multi-Site Research**

**11.1** This is not a multi-site research project.

**11.2** Adverse events, problems, interim results, data and safety monitoring reports and study closure will be reported to the UNM HSC IRB

**11.3** This is not an FDA regulated trial.

